2.0 STUDY OBJECTIVES

2.1 Primary Objective

Estimate the objective overall rate of CR (CR+CRi) for age-adjusted HiDAC (age <60 years: 2 gm/m² IV Q12hours days 1-5; age ≥60 years: 1.5 gm/m² IV Q12hours days 1-5) followed by pembrolizumab 200 mg IV on day 14 in relapsed and refractory AML patients

2.2 Secondary Objectives

- 2.2.1 Estimate the rate of unacceptable toxicity associated with HiDAC followed by pembrolizumab as induction therapy
- 2.2.2 Estimate the objective overall response rates (PR+CR+CRi) for HiDAC followed by pembrolizumab.
- 2.2.3 Characterize the toxicity associated with HiDAC followed by pembrolizumab as induction therapy
- 2.2.4 Characterize the toxicity associated with pembrolizumab 200 mg IV Q3weeks when used as monotherapy maintenance after an initial response to induction phase HiDAC followed by pembrolizumab
- 2.2.5 Estimate the relapse-free survival (RFS) and progression-free survival (PFS) of patients receiving maintenance pembrolizumab
- 2.2.6 Estimate the overall survival (OS) of patients who received induction phase treatment.

[REDACTED]

[REDACTED]

[REDACTED]

[REDACTED]

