1.0 BACKGROUND AND RATIONALE

1.1 Study Synopsis

This is an open-label, single arm, multicenter phase 2 study of standard salvage high dose cytarabine (HiDAC) on days 1 through 5 followed by a single dose of the humanized monoclonal antibody targeted against cell surface receptor programmed cell death-1 (PD-1), pembrolizumab, on day 14 as induction therapy in patients with relapsed and refractory acute myeloid leukemia (AML). Patients who achieve at least a partial response (PR) post-induction will continue on pembrolizumab every 3 weeks for up to 1 year of maintenance therapy. We plan to enroll 37 patients in a Simon's two-stage design.

The hypothesis of this study is that HiDAC followed by pembrolizumab will be effective in relapsed and refractory AML with a combined complete remission (CR)/CR with incomplete recovery (CRi) rate of $\geq 40\%$, superior to a historical control of 20%. We also hypothesize that the rate of unacceptable toxicity associated with HiDAC followed by pembrolizumab will not significantly exceed 20% (see section 2.4.2). Secondary endpoints include toxicity of this combination when used as induction, overall objective response rate (CR+CRi +PR) post-induction, toxicity of pembrolizumab maintenance in those patients with a response after induction, and progression-free survival (PFS), relapse-free survival (RFS) and overall survival (OS) in patients who receive maintenance pembrolizumab. We will also explore for an association between potential immune biomarkers and clinical outcomes with pembrolizumab. The overarching goals of these correlative studies are: 1) to identify and characterize mechanisms involved in T cell dysfunction in AML, 2) to identify potential predictive biomarker candidates to allow better selection of AML patients who may benefit from pembrolizumab, and 3) to identify new pathways that could be targeted to enhance the efficacy of pembrolizumab in AML.

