2.4.2 Secondary Endpoints

- The rate of unacceptable toxicity is defined as drug-related grade 3 non-hematologic toxicity (with exception of infusion reactions, rash, fever, infection, nausea, fatigue, and anorexia) persisting for >7 days with supportive care, or any drug-related non-hematologic grade ≥ 4 toxicity (excluding infection). Toxicity will be classified and graded according to National Cancer Institute's (NCI) Common Terminology Criteria for

Adverse Events (CTCAE, version 4.0). Any patient who receives pembrolizumab treatment on this protocol will be evaluable for toxicity.

- Clinician assessed toxicity of HiDAC followed by pembrolizumab, and toxicity of pembrolizumab maintenance monotherapy classified and graded according to NCI CTCAEv4
- PR+CR+CRi as determined by International European LeukemiaNet Guidelines in AML²¹
- RFS will be defined as time from day 1 of CR/CRi to relapse or death from any cause.
- PFS will be defined as time from day 1 of response (i.e., PR/CR/CRi) to progression or death from any cause.
- OS will be defined as time from day 1 of treatment until date of last known follow up or death of any cause.

[REDACTED]

[REDACTED]

[REDACTED]

[REDACTED]

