4.3 Maintenance Phase

Patients who achieve a PR, CR, or CRi (see section 6.9) will receive pembrolizumab 200 mg IV Q3weeks on an outpatient basis. In order to qualify for pembrolizumab maintenance, all patients will be required to meet laboratory eligibility criteria as outlined in Section 3.1.7 and prior drug-related toxicities must have resolved to \leq grade 1 or baseline. Any patient experiencing unacceptable toxicity during induction, as defined in section 2.4.2, will not be eligible for maintenance, but will be discontinued from protocol-directed therapy and followed-up per protocol. In those who have achieved a CR or PR, pembrolizumab maintenance will begin 10-60 days following full hematologic recovery (absolute neutrophil count \geq 1,000/mcL and platelet count \geq 100,000/mcL). Patients who achieve CRi will begin maintenance pembrolizumab 10-60 days following a bone marrow biopsy disease assessment after induction phase (a repeat bone marrow biopsy should be performed if CRi patients subsequently achieve full hematologic recovery prior to pembrolizumab maintenance, as detailed in Section 4.2: Induction Phase). Patients eligible to receive maintenance therapy should begin maintenance as early as possible (\geq 10 days after hematologic recovery occurs, and once recovery from drug-related toxicities \leq grade 1 or baseline). Those who do not receive maintenance therapy by day 60 of hematologic recovery or by day 60 of post-induction bone marrow biopsy in CRi patients will be taken off study protocol.

All patients who continue pembrolizumab maintenance therapy will have disease assessments with bone marrow biopsies after every 4 cycles of treatment (i.e., every 12 weeks) for the first year, and then after every 6 cycles of treatment (i.e. every 18 weeks) during years 1-2. If there is suspicion for disease progression, a disease assessment via bone marrow biopsy will occur at any time during the maintenance phase. Patients will continue pembrolizumab 200 mg IV Q3weeks

for up to 2 years (i.e., 34 cycles of treatment) until disease progression, unacceptable toxicity, receipt of allogeneic stem cell transplantation or investigator and/or patient chooses to discontinue treatment.

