6.9.2 Relapse-Free Survival

Relapse-free survival (RFS) will be defined as time from CR or CRi until relapse or death. Relapse will be defined as bone marrow blasts $\geq 5\%$ in a patient who initially achieved a CR or CRi after induction phase. Patients who undergo an allogeneic stem cell transplant will be censored for RFS.

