8.3 Data Analysis Plans

The primary endpoint of this study is the overall CR rate (CR+CRi) after HiDAC salvage followed by pembrolizumab on day 14. Responses will be assessed by standard international European LeukemiaNet Guidelines.²¹

Secondary endpoints include the following:

- Rates of unacceptable toxicity defined as any drug-related grade 3 non-hematologic toxicity (exceptions: fever, rash, infection, infusion reactions, nausea, fatigue and anorexia) lasting for >7days despite supportive care, or any drug-related grade ≥ 4 non-hematologic toxicity (excluding infection)
- Clinician assessed toxicity of HiDAC followed by pembrolizumab will be classified and graded according to NCI CTCAE, version 4.0.
- Objective overall response rates will be defined as PR+CR+CRi as determined by international European LeukemiaNet Guidelines in AML.²¹
- Clinician assessed toxicity of pembrolizumab maintenance will be classified and graded according to NCI CTCAE, version 4.0
- RFS will be defined as time from day 1 of CR/CRi to relapse or death from any cause.
- PFS will be defined as time from day 1 of response (i.e., PR/CR/CRi) to progression or death from any cause.
- OS will be defined as time from day 1 of treatment until date of last known follow up or death of any cause.

Survival distributions will be summarized using the method of Kaplan and Meier. We will report median time where possible. All demographic and analytic data will be summarized by descriptive statistics. Categorical data will be summarized using frequency tables while summary statistics such as means, medians, standard deviation, range, etc., will be provided for continuous data. 95% confidence intervals will be reported as well.

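### RFS and PFS are assigned to maintenance recipients but timed from response; name one analysis set and match it to the time origin

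*Combined protocol and SAP*

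**What the plan says.** **Set.** Objective 2.2.5 is to "Estimate the relapse-free survival (RFS) and progression-free survival (PFS) of patients receiving maintenance pembrolizumab". The synopsis (1.1) lists PFS together with "relapse-free survival (RFS) and overall survival (OS) in patients who receive maintenance pembrolizumab". Section 6.9, the parent of the PFS and RFS definitions, instead makes everyone who received pembrolizumab in induction evaluable for response and progression. Section 8.3 names no set for RFS or PFS.

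**Origin.** Section 2.4.2: "RFS will be defined as time from day 1 of CR/CRi to relapse or death from any cause". Section 6.9.2: "Relapse-free survival (RFS) will be defined as time from CR or CRi until relapse or death". Section 8.3: "PFS will be defined as time from day 1 of response (i.e., PR/CR/CRi) to progression or death from any cause". Section 6.9.1 times PFS in the same way.

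**Estimator.** Section 8.3: "Survival distributions will be summarized using the method of Kaplan and Meier". It mentions no landmark, delayed entry or restart of the clock.

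**Wait.** Section 4.3 says that for CR and PR "pembrolizumab maintenance will begin 10-60 days following full hematologic recovery". For CRi the same window runs from the post-induction marrow. Footnote 3 of the Time and Events table agrees, but section 8.1 gives 10-30 days. Section 4.3 adds: "Patients eligible to receive maintenance therapy should begin maintenance as early as possible". Under section 4.6, relapse or progression ends protocol therapy.

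**The concern.** Read together under objective 2.2.5, these sections let a patient into the RFS/PFS set because of something that happens after that patient's clock has started. A responder who dies or has a recognised relapse before the first maintenance dose never enters. A responder who reaches maintenance brings the whole wait along as follow-up in which no such event could have been counted. This is immortal time, and plain Kaplan-Meier does nothing about it.

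Maintenance is given to prevent or delay relapse (section 1.6), and RFS and PFS are its efficacy summaries. The trial has no concurrent control, so a reader may set the medians beside the response durations in section 1.3. A curve labelled as time from response but conditional on reaching maintenance does not describe all responders.

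**Working it through.** The documents give no target, assumption or sample size for RFS or PFS, so there is no plan figure to reproduce for these endpoints. The primary design does reproduce. With 19 + 18 patients, continuation above 4 CR/CRi/PR and rejection at 12 of 37, exact calculation gives type 1 error 4.7-5.0% and power 84.1-85.8% for PR rates from 0 to 0.05. Nothing below touches it.

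**Inputs**
- True median from response: 5 months. This is an assumption, borrowed from the historical response duration in section 1.3 (a different HiDAC schedule).
- Wait G: fixed at 10 days, uniform on 10-30 days (8.1), or uniform on 10-60 days (4.3). The distributions are assumptions. Response is taken as dated at recovery or at the marrow, and a month as 30.44 days.
- Shape: exponential, S(t) = 2^(-t/5), with S(6) = 43.5%; or Weibull with shape 1.5 and the same median, S(6) = 40.2%, for a low hazard just after a remission marrow.
- Events in the wait: either all are excluded, or half still enter because nobody has recognised them.

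**Formulas**
- Keep = E[S(G)]. If half of the gap events enter, Keep = 1 - 0.5 × (1 - E[S(G)]).
- Beyond the longest wait the reported curve is S*(t) = S(t)/Keep.
- Reported median: 5 × (1 - log2 Keep) for the exponential, and 5 × (1 - log2 Keep)^(1/1.5) for the Weibull.
- Example, 10 days, exponential: Keep = 2^(-0.3285/5) = 0.9555; median = 5 × 1.0657 = 5.33 months; S*(6) = 0.435/0.9555 = 0.456.

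**Results: Keep, reported median in months, and change in the six-month rate in points**

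| Wait | Exponential, all excluded | Exponential, half enter | Weibull 1.5, all excluded | Weibull 1.5, half enter |
|---|---|---|---|---|
| 10 days | 0.956; 5.33; +2.0 | 0.978; 5.16; +1.0 | 0.988; 5.06; +0.5 | 0.994; 5.03; +0.2 |
| 10-30 days | 0.913; 5.65; +4.1 | 0.957; 5.32; +2.0 | 0.967; 5.16; +1.4 | 0.983; 5.08; +0.7 |
| 10-60 days | 0.855; 6.13; +7.4 | 0.927; 5.54; +3.4 | 0.923; 5.38; +3.4 | 0.961; 5.19; +1.6 |

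At other true medians, a 10-day wait with exponential times and all gap events excluded turns 3 months into 3.3 and 9 months into 9.3.

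**Against sampling error.** At a 40% CR/CRi rate there are 0.4 × 37 = 14.8 responders. Multiplying by Keep in the first column leaves 14.1, 13.5 and 12.6. The 95% half-width at six months, 1.96 × sqrt(S*(6)(1 - S*(6))/n), is 26.0, 26.6 and 27.6 points, before any censoring. The largest shift in the table is 7.4 points.

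**Timing from maintenance day 1.** Under the exponential the median is 5.0 for every wait. Under the Weibull with all gap events excluded it is 4.73, 4.51 and 4.24 months. The first result reflects the memoryless property only; it does not show that this origin recovers the from-response median.

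**The case against.** The strongest reply is that the plan does not commit itself to the biased analysis. Section 6.9 has a wider evaluable set, section 6.9.2 defines relapse in any patient with CR or CRi after induction, and 8.3 restricts nothing. Run on all responders, the analysis has no guaranteed time. This stands: a reader might infer that upward bias is built into the plan, and the documents do not support that. They support an unresolved set, with bias if 2.2.5 is followed. Section 6.9 says who is evaluable and does not displace the objective, so the sections still have to be reconciled.

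The effect may also be small. Sites are told to start early. The next routine marrow comes only after maintenance cycle 4 (section 6.4.1.2), so unsuspected early relapses can still enter. A PR that becomes CR on maintenance has no wait in its RFS time, although its PFS time keeps one. All of this stands, and the right-hand column of the table shows the result.

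Finally, an estimate for maintenance recipients is a legitimate aim, and 2.2.5 labels the set openly. That is true, but the aim needs an origin or an entry rule that fits it. A wide confidence interval does not remove a systematic shift.

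**Conclusion.** The point holds as an inconsistency between set and time origin, at low priority. If 2.2.5 governs, the guaranteed-time component is upward in every case examined. For an assumed true median of 5 months the reported median is about 5.0-5.2 months (Weibull shape 1.5, half of gap events entering) or 5.3-6.1 months (exponential, all gap events excluded). Shape, wait distribution and the 5-month median are all assumptions.

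Two stronger readings are tempting. One is that reported RFS and PFS will be inflated on balance. The documents do not support this: responders are also kept out of maintenance for unacceptable induction toxicity (section 4.3) and may go straight to transplant, a selection of unknown direction. The other is that restarting the clock at maintenance corrects the from-response median; under the Weibull case it gives a lower figure, because it answers a different question.

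The endpoints are descriptive, with no hypothesis or comparator. The primary test and the 37 patients are unaffected.

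**What to change.** In 2.2.5, the synopsis and 8.3, name the set and match it to the origin, and reconcile this with section 6.9. Either:

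- **(a)** report RFS in all CR/CRi and PFS in all PR/CR/CRi patients from response, whether or not maintenance is given; or
- **(b)** for maintenance recipients, keep the response origin with delayed entry at maintenance day 1, stating that the estimate is conditional on being event-free at the earliest entry; or time from maintenance day 1 and label it as a different estimand.

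With either option, report how many responders did not start maintenance, by reason (relapse, death, toxicity, transplant, other). Reconcile the maintenance-start windows in 4.3 and 8.1.

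**Cost.** Wording in three places, at most one further Kaplan-Meier analysis, and one count table. RFS and PFS may read shorter. Under (b) with delayed entry, the early risk sets will be very small with some 13-14 patients.

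Option (a) has further costs. Non-starters have marrows only on suspicion (Time and Events footnote 11), while recipients have one after every 4th cycle in year 1, so relapse is ascertained unequally. Responders going straight to transplant are censored (6.9.1, 6.9.2). Section 4.3 takes those not started by day 60 off study, whereas footnote 3 keeps them in follow-up; these must be reconciled. Section 6.6 needs progression added to agree with 4.7. PR patients who never start maintenance need a stated blast baseline, because 6.9.1 takes it from the start of maintenance.

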2.4 Endpoints

2.4.1 Primary Endpoint

The rate of CR+CRi as defined by the International European LeukemiaNet Guidelines in AML²¹

2.4.2 Secondary Endpoints

- The rate of unacceptable toxicity is defined as drug-related grade 3 non-hematologic toxicity (with exception of infusion reactions, rash, fever, infection, nausea, fatigue, and anorexia) persisting for >7 days with supportive care, or any drug-related non-hematologic grade ≥ 4 toxicity (excluding infection). Toxicity will be classified and graded according to National Cancer Institute's (NCI) Common Terminology Criteria for

Adverse Events (CTCAE, version 4.0). Any patient who receives pembrolizumab treatment on this protocol will be evaluable for toxicity.

- Clinician assessed toxicity of HiDAC followed by pembrolizumab, and toxicity of pembrolizumab maintenance monotherapy classified and graded according to NCI CTCAEv4
- PR+CR+CRi as determined by International European LeukemiaNet Guidelines in AML²¹
- RFS will be defined as time from day 1 of CR/CRi to relapse or death from any cause.
- PFS will be defined as time from day 1 of response (i.e., PR/CR/CRi) to progression or death from any cause.
- OS will be defined as time from day 1 of treatment until date of last known follow up or death of any cause.

[REDACTED]

[REDACTED]

[REDACTED]

[REDACTED]

3.0 PATIENT ELIGIBILITY

3.1 Inclusion Criteria

Patients must meet all of the following inclusion criteria to participate in this study:

- 3.1.1 Willing and able to provide written informed consent for the trial
- 3.1.2 ≥ 18 years and ≤ 70 years of age on day of signing informed consent
- 3.1.3 ECOG Performance Status 0-1
- 3.1.4 Have histologically or cytologically confirmed recurrent AML as defined by $\geq 5\%$ myeloblasts in the bone marrow aspirate and/or biopsy
- 3.1.5 Must have received at least 1 cycle of induction therapy for front-line AML including:
 - cytarabine continuous infusion + anthracycline +/- cladribine or etoposide for 1 or 2 cycles OR
 - liposomal cytarabine and daunorubicin (CPX-351) OR
 - high dose cytarabine with or without fludarabine OR
 - cladribine or clofarabine OR
 - ≥ 4 cycles of azacitidine/decitabine OR
 - the equivalent experimental therapy (the latter as confirmed by the PI)
- 3.1.6 Cytoreduction allowed with hydroxyurea and/or leukapheresis for up to 14 days prior to D1 of treatment under LCCC1522. Patients must be off hydroxyurea for ≥ 12 hours prior to D1 of treatment under LCCC1522
- 3.1.7 Demonstrate adequate organ function as defined in the table below. All screening labs should performed within 14 days of D1 of treatment under LCCC1522.

System	Laboratory Value
Renal	
Serum creatinine OR Measured or calculated ^a creatinine clearance (GFR can also be used in place of creatinine or CrCl)	≤ 1.5 X upper limit of normal (ULN) OR ≥ 60 mL/min for subject with creatinine levels > 1.5 X institutional ULN
Hepatic	
Serum total bilirubin	≤ 1.5 X ULN unless due to Gilbert's Disease, hemolysis or leukemic infiltration OR Direct bilirubin \leq ULN for subjects with total bilirubin levels > 1.5 ULN
AST (SGOT) and ALT (SGPT)	≤ 5 X ULN
Coagulation	
International Normalized Ratio (INR) or Prothrombin Time (PT)	≤ 1.5 X ULN unless subject is receiving anticoagulant therapy as long as PT or PTT is within therapeutic range of intended use of anticoagulants or patient has disseminated intravascular coagulation

Amendment 07

Activated Partial Thromboplastin Time (aPTT)	deemed by investigator to be due to leukemia ≤1.5 X ULN unless subject is receiving anticoagulant therapy as long as PT or PTT is within therapeutic range of intended use of anticoagulants or patient has disseminated intravascular coagulation deemed by investigator to be due to leukemia
^a Creatinine clearance should be calculated per institutional standard.	

3.1.8 Female subject of childbearing potential should have a negative urine or serum pregnancy within 72 hours prior to receiving the first dose of HiDAC treatment and again prior to D1 of pembrolizumab treatment. If the urine test is positive or cannot be confirmed as negative, a serum pregnancy test will be required.

3.1.9 Female subjects of childbearing potential should be willing to use adequate method of contraception as outlined in Section 4.2.2.1 - Contraception for the course of the study through 120 days after the last dose of study medication. Subjects of childbearing potential are those who have not been surgically sterilized or have not been free from menses for > 1 year. The two birth control methods can be two barrier methods or a barrier method plus a hormonal method to prevent pregnancy. Subjects should start using birth control from the screening visit throughout the study period up to 120 days after the last dose of study therapy.

Note: Abstinence is acceptable if this is the usual lifestyle and preferred contraception for the subject.

3.1.10 Male subjects must agree to use an adequate method of contraception as outlined in section 4.2.2.1 – Contraception, starting with D1 of HiDAC through 120 days after the last dose of study therapy.

Note: Abstinence is acceptable if this is the usual lifestyle and preferred contraception for the subject.

3.1.11 As determined by the enrolling physician or protocol designee, ability of the patient to understand and comply with study procedures

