4.2.2.1 Contraception

Pembrolizumab may have adverse effects on a fetus in utero. Furthermore, it is not known if pembrolizumab has transient adverse effects on the composition of sperm. For this trial, male subjects will be considered to be of non-reproductive potential if they have azoospermia (whether due to having had a vasectomy or due to an underlying medical condition).

Female subjects will be considered of non-reproductive potential if they are either:

(1) postmenopausal (defined as at least 12 months with no menses without an alternative medical cause; in women < 45 years of age a high follicle stimulating hormone (FSH) level in the postmenopausal range may be used to confirm a post-menopausal state in women not using hormonal contraception or hormonal replacement therapy. In the absence of 12 months of amenorrhea, a single FSH measurement is insufficient.);

OR

(2) have had a hysterectomy and/or bilateral oophorectomy, bilateral salpingectomy or bilateral tubal ligation/occlusion, at least 6 weeks prior to screening;

OR

(3) have a congenital or acquired condition that prevents childbearing.

Female and male subjects of reproductive potential must agree to avoid becoming pregnant or impregnating a partner, respectively, while receiving study drug and for 120 days after the last dose of study drug by complying with one of the following:

(1) practice abstinence[†] from heterosexual activity;

OR

(2) use (or have their partner use) acceptable contraception during heterosexual activity.

Acceptable methods of contraception are[‡]:

Single method (one of the following is acceptable):

- intrauterine device (IUD)
- vasectomy of a female subject's male partner
- contraceptive rod implanted into the skin

Combination method (requires use of two of the following):

- diaphragm with spermicide (cannot be used in conjunction with cervical cap/spermicide)
- cervical cap with spermicide (nulliparous women only)
- contraceptive sponge (nulliparous women only)
- male condom or female condom (cannot be used together)
- hormonal contraceptive: oral contraceptive pill (estrogen/progestin pill or progestin-only pill), contraceptive skin patch, vaginal contraceptive ring, or subcutaneous contraceptive injection

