[†]Abstinence (relative to heterosexual activity) can be used as the sole method of contraception if it is consistently employed as the subject's preferred and usual lifestyle and if considered acceptable by local regulatory agencies and ERCs/IRBs. Periodic abstinence (e.g., calendar, ovulation, sympto-thermal,

post-ovulation methods, etc.) and withdrawal are not acceptable methods of contraception.

‡If a contraceptive method listed above is restricted by local regulations/guidelines, then it does not qualify as an acceptable method of contraception for subjects participating at sites in this country/region.

Subjects should be informed that taking the study medication may involve unknown risks to the fetus (unborn baby) if pregnancy were to occur during the study. In order to participate in the study subjects of childbearing potential must adhere to the contraception requirement (described above) from the day of study medication initiation (or 14 days prior to the initiation of study medication for oral contraception) throughout the study period up to 120 days after the last dose of trial therapy. If there is any question that a subject of childbearing potential will not reliably comply with the requirements for contraception, that subject should not be entered into the study.

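### The definition in 3.1.9 that decides who is pregnancy-tested exempts some women whom 4.2.2.1 counts as of reproductive potential

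*Combined protocol and SAP*

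**What the plan says.** Section 3.1.8 sets the testing rule: "Female subject of childbearing potential should have a negative urine or serum pregnancy within 72 hours" of the first HiDAC dose, and again before pembrolizumab. Sections 6.2 and 6.3.3 repeat it with the same trigger term. The Time and Events table (6.1) schedules two tests, pre-study and day 14. Its footnote 7 limits them to cases judged clinically appropriate.

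Section 3.1.9 defines the trigger term: "Subjects of childbearing potential are those who have not been surgically sterilized or have not been free from menses for > 1 year".

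Section 4.2.2.1 approaches the same group from the other side: "Female subjects will be considered of non-reproductive potential if they are either" of three things, any one of which is enough:

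- "postmenopausal (defined as at least 12 months with no menses without an alternative medical cause";
- one of a list of operations, ending with "bilateral salpingectomy or bilateral tubal ligation/occlusion, at least 6 weeks prior to screening";
- "have a congenital or acquired condition that prevents childbearing".

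The section requires contraception of everyone of reproductive potential. It then says that "subjects of childbearing potential must adhere to the contraception requirement (described above" and continues with an entry bar that begins "If there is any question that a subject of childbearing potential will not reliably comply with the requirements for contraception".

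**The concern.** Two definitions cover one group of women and do not agree. The definition in 3.1.9 is attached to testing. It ignores the cause of amenorrhea and the time since surgery, and 4.2.2.1 makes exemption depend on both.

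A site that follows 3.1.9 could therefore leave a woman untested at both scheduled points although 4.2.2.1 regards her as able to conceive. What is at stake is an unrecognized early pregnancy at the start of treatment with HiDAC and then pembrolizumab. Section 5.1.6 warns that pembrolizumab may harm a fetus.

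**Working it through.** The plan gives no figure to reproduce. The check is to apply the two definitions to the same women.

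**Inputs.** From 3.1.9: S = surgically sterilized; F = more than 1 year without menses. From 4.2.2.1: P = 12 months or more without menses and no other medical cause; S6 = listed surgery at least 6 weeks before screening; C = a condition that prevents childbearing.

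**Rules for who is tested.**

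- 3.1.9, ordinary reading (either feature exempts): not S and not F.
- 3.1.9, literal reading (either negative is enough to include): not S, or not F.
- 4.2.2.1, if it governed testing: not (P or S6 or C).

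**Women on whom the rules differ** (C absent unless stated):

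| Woman | 3.1.9 ordinary | 3.1.9 literal | 4.2.2.1 |
|---|---|---|---|
| A. Not sterilized; more than 1 year without menses, medical cause | no test | test | reproductive potential |
| B. Sterilized less than 6 weeks before screening; menses within the past year | no test | test | reproductive potential |
| C. Sterilized less than 6 weeks before screening; more than 1 year without menses, medical cause | no test | no test | reproductive potential |
| D. Not sterilized; exactly 12 months without menses, natural | test | test | non-reproductive |
| E. Not sterilized; more than 1 year without menses, natural | no test | test | non-reproductive |
| F. Sterilized at least 6 weeks before screening; menses within the past year | no test | test | non-reproductive |
| G. Not sterilized; menses within the past year; condition that prevents childbearing | test | test | non-reproductive |

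**Result, ordinary reading.** Women in rows A to C are exempt from testing under 3.1.9 but of reproductive potential under 4.2.2.1. Rows D and G go the other way: the test is required, but 4.2.2.1 would not call for it. Row D arises because 3.1.9 asks for more than 1 year and 4.2.2.1 for 12 months or more.

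**Result, literal reading.** Rows A and B are tested. Rows D to G are tested without need. Only row C, with both features, is still missed. The main effect of this reading is over-testing.

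Neither reading reproduces 4.2.2.1, and the safety gap belongs mainly to the ordinary one. The rows are kinds of woman and say nothing about how many would enrol.

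**The case against.** The strongest reply is that the sections are meant to be read together. Section 3.1.9 sends the reader to 4.2.2.1, and 4.2.2.1 itself uses the term childbearing potential when it refers back to its own requirement. A site could take 3.1.9 as a short summary and 4.2.2.1 as the full rule. This is partly right: the back-reference does tie the two terms to one population. But the pointer in 3.1.9 is to the method of contraception, after which 3.1.9 gives its own, different definition. No sentence says which definition governs testing.

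The affected group is also narrow. Medically caused amenorrhea matters only if the cause does not itself prevent childbearing. Recent sterilization means surgery shortly before screening in a patient with recurrent AML, and after hysterectomy or bilateral oophorectomy there is little real risk. The gap there is mainly about recent tubal procedures. All of this stands and supports a low severity.

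Other safeguards limit the harm. Section 3.2.13 excludes pregnant women, 4.2.2.1 still requires contraception of the women in rows A to C and bars entry if compliance is doubtful, and nothing forbids a test. But contraception does not detect a pregnancy that already exists, and an exclusion for pregnancy depends on finding it. Footnote 7 leaves room for judgement without naming a group.

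A reader might infer that the plan admits pregnant women, or frees these women from contraception. It does neither. A reader might also infer that both readings of 3.1.9 are equally unsafe. They are not, because the literal one mostly adds tests.

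**Conclusion.** The point holds as a conflict between two stated rules. On its ordinary reading, 3.1.9 exempts from both scheduled pregnancy tests some women whom 4.2.2.1 treats as of reproductive potential. The mismatch at exactly 12 months and the ambiguous 'or' are lesser faults in the same sentence.

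Severity is minor. Those affected are a small subset of the 37 planned patients, and the documents give no number. The sample size, the primary endpoint and its analysis are untouched.

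The conclusion assumes that sites read 3.1.9 in the ordinary way and that 4.2.2.1, the more detailed text, states the intended rule. That medically caused amenorrhea will occur here is a clinical assumption. It is plausible because 3.1.5 requires prior AML therapy and 3.2.20 allows a prior autologous transplant.

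**What to change.** Delete the definition sentence in 3.1.9. State once that childbearing potential, wherever it appears (3.1.8, 3.1.9, 4.2.2.1, 6.2, 6.3.3 and Time and Events footnote 7), means not meeting the 4.2.2.1 definition of non-reproductive potential. In footnote 7, replace the clinical-appropriateness qualifier with that term. Nothing else in 3.1.9 has to change for this point.

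The cost is a wording amendment, with matching consent text if needed. Each newly included woman has at most two scheduled tests: one before HiDAC and one before pembrolizumab. Some women are spared tests, such as those in rows D and G.
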